Data to be acquired at baseline: Child: Age, gender, spectacles ownership, presenting and best corrected visual acuity in both eyes; refractive error in both eyes; distance of child's home from nearest Vision Center; brief spectacle attitude questionnaire; brief family Socio-Economic Status (SES) questionnaire[15]. Teacher: Brief questionnaire on attitudes and knowledge towards spectacles. Program: Survey of all program costs for screening and distribution for each model. Our cost-effectiveness analysis will be from the Program rather than the societal perspective, but the investigators will capture travel cost info from a 1% sample of randomly-selected children/families and capture information about teacher time spent in meeting with parents, sending notes to parents and encouraging children to wear spectacles in a 1 % random sample of Referral group teachers, in order to perform a sensitivity analysis of the impact of including these costs. Regarding programs costs, in the School model, where the optometrist team does the screening at school, the program

cost will be calculated by taking the cost of the primary and secondary screening, cost of the spectacles, and cost of delivering them. In the Referral model, the investigators will include the cost of primary screening, secondary screening at the vision centres and the cost of spectacles. In the Cost recovery model, the cost recovered by selling the spectacles (difference between retail price and cost of spectacles to the hospital) will be subtracted from the program cost. School: Urban versus rural, public versus private, size of the school, SES of community, and distance of the school from nearest Vision Center.

[figure not shown]
Follow-up schedule and follow-up data: Self-reported and observed spectacle wear to be ascertained at an un-announced follow-up at school 3 months after distribution of spectacles. Additionally, the following data for the Referral groups will be collected from the referral centre and verified from the children in a random sample of 10% of children: Did they visit the referral centre? Did they receive free spectacles? Did they elect to purchase upgrade spectacles? (in the Cost Recovery group). Children in the Referral groups not having received spectacles at the referral centres will receive them now, and so their visual acuity with spectacles and refractive power in each eye will be measured and recorded.

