Data collection: An experienced project coordinator will be responsible for data collection and follow-up. The project coordinator will be thoroughly trained on the completion of the data collection forms.

Data Management Plan: The baseline data will be entered and stored in the database (“Reachsoft”), which is password protected. Other data for the study will be collected and entered by an external data entry operator and sent to the project manager to store it in a password-protected system. The collected data will be analyzed in de-identified fashion by the study statistician in India.

A copy of the final study data will be shared with Queen's University Belfast (QUB) under the data sharing and protection outlined in a Memorandum of Understanding. The final dataset will be stored in the QUB database under QUB custody. The study team will have access to the data for research and analyses purposes only. Data will be stored for 5 years after the end of the study.

- **Study Flow:**

Data Analytic Plan: Data will be analysed using STATA 15. The primary and secondary outcomes will be compared between the three randomized groups using an intention to treat approach with and without adjustment for the baseline child, school and teacher factors listed above. Our primary outcome is cost-effectiveness (cost per child identified needing spectacles, who gets and is still wearing them 3 months later). The investigators have two hypotheses about this primary outcome:

Primary hypothesis: The improved Referral model which involves teachers contacting families will sufficiently improve uptake that this Referral model will be more cost-effective than the School model.

Proposed analysis: Cost per child identified needing spectacles (program perspective, as above), who gets and is still wearing them 3 months later, compared between School and Referral model.

Secondary hypothesis: Cost recovery from the Referral + Cost Recovery Model will make this more cost-effective than either of the other models.

Proposed analysis: Cost per child identified needing spectacles, who gets and is still wearing them 3 months later, compared between the Referral + Cost Recovery and other groups.

The investigators will also do a stratified analysis comparing the main outcome between groups at each of the 3 participating hospitals. Additional stratified analyses / balancing of the main outcome between groups will be done for public versus private schools and rural versus urban schools.

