The investigators will be using Latent class regression analysis and Finite mixture models to analyze the main outcome.

Monitoring: A dedicated Project Manager, [name], will be responsible for the overall planning, implementation, coordination, and monitoring and evaluation in the project. She will recruit a local project assistant at each site to coordinate all activities at the community level and at the base hospital and Vision Centers; ensure that appropriate planning is done for organizing and implementing screening activities; and coordinate availability of trained manpower, equipment, and facilities. [name] will interact with Orbis India Project Managers for the REACH program.

Research advisors [name], [name], and [name] each has decades of familiarity with refractive error research in children, and all have engaged in multiple research projects in India. Additionally, [name] has worked with Orbis since 2009 and is now its Director of Research.

Ethical considerations: Ethical approval has been received from two of the partners in India and Queen's University Belfast and will be sought from the additional partner. In the two Referral model groups, children who need to go to the facility to get spectacles but do not do so within the three-month period will receive free spectacles at closeout, so that no child requiring treatment will be left untreated.

Conditions

Conditions: Childhood Refractive Error

Keywords: Child, refractive error, myopia, school screening, cost effectiveness, India

Study Design: Cluster-randomised, investigator-masked trial

Study Type: Interventional

Primary Purpose: To determine the most cost-effective approach to school-based vision screening and spectacles delivery in India . Health Services Research

Study Phase: N/A

Interventional Study Model: Parallel Assignment

Randomization, Interventions: This is a cluster randomized trial, with eligible children allocated to the intervention that their school was randomized to receive. This will be one of the following three:

School Model (47 schools): Vision screening will be carried out by the vision screeners; refraction will be done at the schools by refractionists; and children who need them will be given free spectacles at the school within two weeks.

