Program cost-effectiveness

Program cost per child identified with correctable refractive error, who receives spectacles and wears them at an un-announced visit 3 month after distribution. Income from sales of spectacles in the "Referral + Cost Recovery" group will be subtracted from the program costs. The groups will be compared, with and without adjustment for baseline characteristics.

[Time Frame: 13 months]

Secondary Outcome Measures:

Proportion of children receiving spectacles who are wearing them at the time of un-announced 3-month follow-up

Purchase rates of upgrade spectacles in the Referral + Cost Recovery Group

Teacher and student reports of rates of teacher interventions in the two Referral groups (contact of parents to complete referral, encouraging children to wear spectacles)

Baseline visual acuity with spectacles

Refractive power of spectacles

[Time Frame: 12 months]

Eligibility

Minimum Age: 10 Years

Maximum Age: 15 Years

Sex: All

Gender Based: No

Accepts Healthy Volunteers: No

Criteria:

Inclusion Criteria:

Eligibility: Enrolment criteria:

- Children in randomly-selected 6th to 10th grades in selected schools with presenting visual acuity (that is, wearing spectacles if spectacles are owned at baseline) $\leq 6/9.6$ (0.2 LogMAR) in either eye.
- Children who already own spectacles will be requested to bring their spectacles on the day of screening, and children whose vision with existing spectacles meets study criteria will be eligible.
- Entry into the trial only requires that a child fail vision screening, which is assessed in the same way for all three randomized groups.

Exclusion Criteria:

- Parents returning the form indicating they do not wish their child to participate;
- no Vision Center within 50 km of the child's home (a rare occurrence in the REACH network).
- If the child is incapable of completing visual acuity screening in both eyes for any reason.

References

Citations:

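### Is the date of the 3-month spectacle-wear visit left unset in the two Referral groups?

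*Combined protocol and SAP*

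**What the plan says.** Three places set the wear visit, and they agree.

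- Follow-up schedule and follow-up data: "Self-reported and observed spectacle wear to be ascertained at an un-announced follow-up at school 3 months after distribution of spectacles".
- Primary Outcome Measure: the child receives spectacles and "wears them at an un-announced visit 3 month after distribution". It carries the label "Time Frame: 13 months"; the secondary outcomes carry a 12-month label.
- Data Analytic Plan: cost per child "who gets and is still wearing them 3 months later, compared between School and Referral model".

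Supply differs by group. In the School Model, "children who need them will be given free spectacles at the school within two weeks". In the two Referral groups spectacles are dispensed at a centre when the family attends, and teachers contact families who have not come.

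Two places cover Referral children who never collect. The follow-up paragraph says "Children in the Referral groups not having received spectacles at the referral centres will receive them now". Ethical considerations says that those who need to attend but "do not do so within the three-month period will receive free spectacles at closeout". The items taken from the referral centre are "Did they visit the referral centre? Did they receive free spectacles? Did they elect to purchase upgrade spectacles"; a dispensing date is not among those named.

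**The concern.** Counting from distribution works easily when a whole school is supplied at about the same time. It is harder when children collect one by one. A single school visit cannot fall exactly three months after every child's own collection, and a child who never collected has no such date. The three-month period under Ethical considerations must therefore start somewhere else, and the text gives no start. Nor does it say that the visit at which non-collectors are supplied (the word used is 'now') is the same as closeout.

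If there is one school visit at the end of a three-month period that starts at screening, late collectors have had spectacles for less than three months. Teacher contact is meant to bring in families who did not come at first, so some late collection is expected. Time in possession would then differ between groups, and the wear part of the primary outcome would partly reflect when it was measured. The Sample size section assumes 40% wear in both models, and its break-even uptake depends on that equality.

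**Working it through.** **1. The plan's own break-even.** Inputs from Sample size: US$1.30 and US$0.80 per child screened, 95% uptake in the School Model, 40% wear in both models, 3% prevalence.

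- Break-even Referral uptake = (0.80 × 0.95 × 0.40) / (1.30 × 0.40) = 0.5846. The plan states 58.5%, so it reproduces.
- Cost per wearer, School: 1.30 / (0.03 × 0.95 × 0.40) = US$114.04.
- Cost per wearer, Referral at 65% uptake: 0.80 / (0.03 × 0.65 × 0.40) = US$102.56.

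**2. How far Referral wear would have to move.** At 65% uptake the two costs are equal when Referral wear = (0.80 × 0.95 × 0.40) / (1.30 × 0.65) = 0.304 / 0.845 = 36.0%, about 4 points below plan. The shift could also go the other way: at 42% wear the break-even uptake falls to 0.304 / (1.30 × 0.42) = 55.7%. The document has no figure for wear against time since dispensing, so neither direction can be preferred.

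**3. Who could be affected.** Children needing spectacles: 300 × 0.03 = 9 per school, 47 × 9 = 423 per group. At 65% uptake, 275 collect and 148 do not. The 148 had no study spectacles before the visit, so they add cost and no wearers whenever it is held. Only the 275 collectors have wear that timing could move, and among them only those who collect late.

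The late share is not given. Suppose, for illustration, that all uptake above unprompted attendance *a* is late, and nothing else is: share = (0.65 − *a*) / 0.65. For the average to fall 4 points, wear among late collectors must fall by 4 / share.

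| Unprompted attendance | Late share of collectors | Fall needed among late collectors |
|---|---|---|
| 1/3 (low end implied by Problems with current models) | 49% | 4 / 0.487 ≈ 8 points |
| 50% (assumed) | 23% | 4 / 0.231 ≈ 17 points |
| 58.5% (assumed) | 10% | 4 / 0.10 = 40 points, i.e. no late collector wearing |

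**4. Schedules that fit the text.** Let *d* be months from screening to collection, from 0 to 3.

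- One school visit at month 3: possession is 3 − *d*, so 0 to 3 months in the Referral groups, against 2.5 to 3 months in the School Model if its two weeks run from screening.
- A three-month collection period, then one school visit at month 6 (assumed): possession is 6 − *d*, so 3 to 6 months. Nobody falls short of three months, and supplying non-collectors at that visit fits both the follow-up paragraph and Ethical considerations.
- Three months from each child's own collection: every collector is seen at three months, as in the School Model. With 9 × 0.65 = 5.85 collectors per school, this could need up to about 6 visit dates per Referral school, spread over months 3 to 6.

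Possession under three months is therefore one possible schedule. It does not follow from the wording.

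**5. The secondary wear proportion.** If children first supplied at the visit entered the denominator, the planned 40% would become 0.65 × 0.40 = 26%. That reading does not suit an outcome defined at three months after distribution, since those children have only just been supplied.

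**The case for a change.** The strongest case for acting is that the ambiguity is real and touches the primary outcome. In the visible text, distribution is not defined at child or school level for the Referral groups, the three-month period has no stated start, and the wear visit is not expressly equated with closeout. Late collection is built into the teacher intervention, the margin is only about 4 points of wear, and a dispensing date that is never recorded may not be recoverable later.

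The ambiguity stands; the step from it to a defect does not. The anchor is stated in three places. A second clock for non-collectors is inferred from one undated phrase about supply, which does not set the wear visit. A figure stood immediately before the follow-up paragraph and the Study Flow heading is empty; both were lost when the text was extracted, and they are where visit timing would normally be drawn. A team told to visit three months after distribution needs to know when distribution took place, so the anchor implies the date, and the forms that might hold it are not shown. The 12- and 13-month labels do not conflict with a three-month visit: the 12-month one also covers baseline visual acuity, so it reads as a project-level frame.

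**Conclusion.** No change follows. The plan sets the wear visit at three months after distribution, consistently, and a team applying that anchor gets a sound comparison.

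The remaining choice is a fair trade-off. A per-child clock keeps the outcome wording and equalises possession, but may need up to about 6 visits to a Referral school, and later ones may be less of a surprise. A common date per school needs one visit and gives equal observation time by randomised group, in keeping with the intention-to-treat approach. It counts late collection as part of the model's effect, however, and would mean rewording the primary outcome. Neither is clearly better. The order of recording at the visit and the secondary denominator are details that analysts would settle sensibly: the follow-up paragraph already lists wear first, then the referral questions, then supply.

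The size cannot be estimated. The plan's 58.5% reproduces, and Referral wear of about 36% instead of 40% would remove the planned advantage at 65% uptake, but the document does not link wear to time since dispensing. It also names referral compliance, not wear, as the main driver of cost-effectiveness. This conclusion rests on the planning values in Sample size at the minimum school size, on the late-collector shares being illustrations only, and on the unseen figure and study flow not contradicting the stated anchor.

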Sample size: At a refractive error prevalence of 3%, with minimum of 300 children/school, 95% of children receiving spectacles in the School Model, 40% of children wearing them in both the School Model and Referral Model groups at un-announced 3 month visits, a cost of US\$1.30 per child screened in the School Model and US\$0.80 in the Referral Model (all assumptions based on REACH Program data), if 58.5% of families accept referral to receive refraction and spectacles in the Referral Model, this would reach the same cost-effectiveness as the School Model. A total of 141 schools (47 in each of three groups) across three participating hospitals would be sufficient to detect significantly better cost-effectiveness of the Referral Model if 65% of families accept referral for refraction/spectacles, which is the target in our hypothesis; with a power of 90%, an alpha-error of 0.05, and an intracluster correlation coefficient (ICC) (a measure of how similar children are to one another within schools: "clustering") of 0.20.

Randomization: An independent statistician having no contact with participants will generate the randomization sequence using a computer system that is inaccessible until after the school has agreed to join the trial. Schools will be stratified into two groups as Public and private. The schools in each stratified group will be randomly assigned to either the intervention (referral models) or control group (school model) in a 1:1:1 ratio with a block size of three to ensure balance. After randomization, the schools and the children in them will not be masked to their allocated intervention but staff assessing data for the main outcome will not know a child's group assignment.

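### The only method named for the primary outcome does not yield the School v Referral contrast in cost per wearing child, and the analysis plan states no contrast scale, interval, test or allowance for schools

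*Combined protocol and SAP*

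**What the plan says.** The Data Analytic Plan defines the primary outcome as cost per child who needs spectacles, gets them and still wears them at 3 months. For the primary hypothesis, the proposed analysis is this cost, "who gets and is still wearing them 3 months later, compared between School and Referral model". Outcomes are to be compared between the three groups "using an intention to treat approach with and without adjustment for the baseline child, school and teacher factors listed above". There is also a stratified analysis "comparing the main outcome between groups at each of the 3 participating hospitals". The section then adds one sentence on method: "The investigators will be using Latent class regression analysis and Finite mixture models to analyze the main outcome".

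The Primary Outcome Measure entry repeats that the groups will be compared with and without adjustment, and adds no method.

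Clustering appears in the Sample size paragraph, which uses "an intracluster correlation coefficient (ICC) (a measure of how similar children are to one another within schools", set at 0.20. Alpha of 0.05 is given there too. Under Randomization, "Schools will be stratified into two groups as Public and private". Under Data to be acquired at baseline, costs come from a "Survey of all program costs for screening and distribution for each model".

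**The concern.** The outcome is clear enough to compute a point estimate for each arm: total program cost divided by total wearers. What is missing is the step from two point estimates to an inference. The text does not say whether the contrast is a difference or a ratio, how its interval is formed, what test is used, or how the randomised unit enters.

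The one method named does not fill the gap. A latent class or finite mixture model needs a response for each observed unit, and an arm term from which a marginal cost contrast can be read. Cost per wearer is not a property of a child, because a child who does not wear spectacles has no cost per wearer. At school level it is undefined when nobody wears them. An analyst would have to invent the primary analysis, possibly with the data in hand, and the choices available give materially different answers.

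**Working it through.** **Inputs, from the Sample size paragraph.** "At a refractive error prevalence of 3%, with minimum of 300 children/school", so 0.03 × 300 = 9 affected children per school; 47 schools per arm; 95% receipt in the School Model; 40% wear after receipt in both arms; US$1.30 (School) and US$0.80 (Referral) per child screened; ICC 0.20.

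**The plan's own figures.**
- Break-even uptake = (0.80/1.30) × 0.95 = 58.46%, which agrees with the stated 58.5%.
- School cost per wearer = 1.30/(0.03 × 0.95 × 0.40) = US$114.0.
- Referral cost per wearer at 65% uptake = 0.80/(0.03 × 0.65 × 0.40) = US$102.6.
- Ratio = 102.6/114.0 = 0.90. At break-even both arms cost US$114.0 and the ratio is 1.00.

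**Assumptions added.** The ICC applies to wear (the plan does not say which outcome it refers to) and ranges from 0.05 to 0.20. There are 9 to 15 affected children per school, because 300 is a minimum (15 corresponds to 500 pupils at 3%). Wear is beta-binomial. Cost per child screened is fixed.

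**(i) Children analysed as independent.** Design effect DE = 1 + (m − 1) × ICC. Actual type I error of a nominal two-sided 5% test = 2 × (1 − Φ(1.96/√DE)).

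| Children per school (m) | ICC 0.20 | ICC 0.10 | ICC 0.05 |
|---|---|---|---|
| 9 | DE 2.6, 22% | DE 1.8, 14% | DE 1.4, 10% |
| 15 | DE 3.8, 31% | DE 2.4, 21% | DE 1.7, 13% |

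At planning values, wear among affected children is 0.95 × 0.40 = 0.38 (School) and 0.65 × 0.40 = 0.26 (Referral), with 47 × 9 = 423 children per arm. The naive SE of the log ratio is √[(0.62/0.38 + 0.74/0.26)/423] = 0.103. With DE 2.6 it is 0.103 × √2.6 = 0.166, about 1.6 times wider. Around the ratio of 0.90, the 95% intervals are 0.735 to 1.100 (naive) and 0.650 to 1.245 (clustered).

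**(ii) School-level ratios used as the response.** Take break-even, where the true ratio is 1.00. With ICC 0.20 and 9 children per school, the probability of no wearers is 0.108 in a School Model school and 0.276 in a Referral school. That makes 47 × 0.108 ≈ 5 and 47 × 0.276 ≈ 13 schools with no defined value. The mean ratio over the remaining schools, against a true US$114.0 in each arm, is:

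| Setting | School | Referral | Referral/School |
|---|---|---|---|
| ICC 0.20, m = 9 | US$153.8 | US$125.2 | 0.81 |
| ICC 0.20, m = 15 | US$178.7 | US$161.6 | 0.90 |
| ICC 0.10, m = 15 | US$160.6 | US$160.0 | 1.00 |
| ICC 0.05, m = 15 | US$147.2 | US$155.1 | 1.05 |

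Two effects compete. Dropping schools with no wearers lowers the mean. Averaging cost/wearers over schools with few wearers raises it. The second dominates in both arms, and the net effect on the contrast changes sign within the range.

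**Check of the alternative.** The log ratio of arm totals was simulated at break-even, with between-school variance within arm and public/private stratum and a t reference. Its type I error was about 5% (0.048 to 0.052) at ICC 0.20, 0.10 and 0.05 with 9 children per school and 47 schools per arm.

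**The case against.** The plan is not silent. It defines the outcome, the arms compared, intention to treat, adjustment and software. It calls the trial cluster randomised and plans with an ICC, so a competent statistician would probably allow for schools. This stands as far as it goes: the per-arm estimate follows from the text, and nothing says that clustering will be ignored.

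Two stronger readings are tempting and are not supported.

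- A reader might infer that the sponsor plans a child-level test with inflated error. The documents do not state one; they leave it open. The figures in (i) show what one unexcluded choice would cost. At planning values both intervals include 1, so that example does not change the conclusion.
- A reader might infer that losing schools without wearers, which are commoner in the Referral arm, would make Referral look cheaper than it is. Pooling totals after dropping such schools does give 0.81 at ICC 0.20 with 9 per school, but a model of school-level ratios does not estimate that quantity. The mean school ratios put Referral above its true US$114, and the contrast can move either way.

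It is also fair to say that a log ratio with a school-level interval is one acceptable choice among several. The point is that one must be named.

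**Conclusion.** The concern holds and should be settled before analysis. The named method does not deliver the primary contrast, and the scale, interval, test and treatment of schools are unstated. This rests on the text alone and does not depend on the illustrations.

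The sizes are conditional on choices that the plan leaves open. A child-level analysis would have 10% to 31% type I error across the range examined. A model of school-level ratios could move a true ratio of 1.00 to between 0.81 and 1.05, with no predictable direction. The figures in (ii) also assume fixed cost per child screened, whereas the plan's costs include spectacles, which vary with receipt.

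**What to change.** Replace the sentence on latent class and finite mixture models with wording such as:

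> The primary analysis is the ratio (Referral/School) of total program cost divided by total wearers in each arm, with a two-sided 95% CI on the log scale from the between-school variance of costs and wearer counts within arm and public/private stratum, with a t reference. A whole-school bootstrap is a sensitivity analysis. The adjusted analysis uses the same ratio with a school-level jackknife or robust variance, and carries any cost that depends on spectacles received through the adjustment. Latent class or finite mixture models are supportive only.

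Three details need a line each:
- State whether observed or self-reported wear defines a wearer, since the follow-up section collects both.
- Where costs are recorded only by model, apply unit costs to each school's counts, and state that uncertainty in the unit costs is then not captured.
- In the hospital-level comparisons, drop the public/private strata where a cell has fewer than two schools.

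The cost is SAP wording, a little more work in Stata, and intervals wider than naive ones (about 1.6 times at ICC 0.20 with 9 per school). Recruitment, randomisation and visits are unaffected. The documents also differ on whether income or profit from sales is subtracted; that touches only the Cost Recovery comparisons and should be raised separately.

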Potential superiority of optimized Referral Models and improvements for vulnerable children: Recent evidence from a review by [name] and [name][11,12] and trials by [name][13] suggest that various strategies which increase involvement of teachers in the screening process (parent-teacher meetings; short message service (SMS), phone call, or handwritten notes in the students diary from teachers to families who do not complete referrals) can significantly increase the proportion of families following up for care at an outside eye care facility. Therefore, this cluster randomized trial will test an "optimized" model of distribution of spectacles, maximizing teacher involvement, to determine whether this approach can achieve comparable service uptake to fully school-based models at a greater level of cost-effectiveness. High-quality, trial-based evidence that showed that optimized Referral models are both low-cost and high-coverage may provide a strong stimulus to scale up refractive service programs in India and other low-middle income countries (LMICs). These programs can benefit millions of low-income children not currently receiving refractive services, thus improving their access to classroom learning.

This trial will compare two general screening methods: 1. School model and 2. Referral Model. A "Cost model", which is builds on the Referral model but includes the sale of spectacles, will also be included, as a third randomized group. In the School model, refraction occurs at the school and spectacles are given to children at the school, which may yield a higher rate of compliance, but is more expensive and may not be sustainable. On the other hand, the Referral model, where the children are referred to be screened at the vision center or service center may have lower compliance but be less expensive and more likely to be sustainable. This study examines the hypothesis that greater teacher involvement in screening and follow up can improve the compliance of children and families with the examination at the service center in the Referral model. For this reason, the main outcome of the trial is cost-effectiveness (amount spent per child who receives spectacles that improve his/her vision, and which are worn at an un-announced examination three months after distribution). If the teacher intervention can improve compliance in the Referral model,

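### The primary ratio alone does not settle which model is preferable: at the plan's own target, Referral wins on cost per wearer with 32% fewer wearers per child screened, and no listed outcome would show the gap

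*Combined protocol and SAP*

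**What the plan says.** Under Outcome Measures, the primary outcome is "Program cost per child identified with correctable refractive error, who receives spectacles and wears them at an un-announced visit 3 month after distribution". The Data Analytic Plan compares this figure between School and Referral (primary hypothesis), and between Referral + Cost Recovery and the other groups (secondary hypothesis). It plans no difference in cost, difference in wearers, incremental ratio, net benefit or value per extra wearer.

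The background section on optimized Referral Models asks whether the approach "can achieve comparable service uptake to fully school-based models at a greater level of cost-effectiveness". The Sample size section powers the trial for a Referral win if "65% of families accept referral for refraction/spectacles, which is the target in our hypothesis", against "95% of children receiving spectacles in the School Model".

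The listed secondary wear outcome counts only children who received spectacles. Receipt among all children enrolled, or among all who need spectacles, is not a listed outcome. The follow-up section does collect centre attendance and receipt in the Referral groups.

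**The concern.** An average ratio divides each arm's cost by its own wearers. A cheaper arm can have the better ratio while leaving more children in the same schools without spectacles in use. When one option is both cheaper and less effective, the choice depends on what an extra wearer is worth, and the plan gives no such value.

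The trial could therefore report Referral as the most cost-effective model without showing how many fewer children per school end up wearing spectacles, or what School charges for the difference. The conditional wear outcome would look equal in the two arms, so a reader could take uptake to be comparable when it was not.

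**Working it through.** **Inputs, all from the Sample size section**
- "At a refractive error prevalence of 3%, with minimum of 300 children/school"
- "95% of children receiving spectacles in the School Model"; Referral acceptance target 65%
- "40% of children wearing them in both the School Model and Referral Model groups at un-announced 3 month visits", read as a proportion of those who receive spectacles
- Cost in US$: "1.30 per child screened in the School Model" and "0.80 in the Referral Model"
- 47 schools per arm, so 47 × 300 = 14,100 children screened per arm

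**1. Reproduce the plan's break-even.** Cost per wearer = cost per child screened ÷ (prevalence × receipt × wear). With equal wear, the two arms' ratios are equal when acceptance = 0.95 × 0.80/1.30 = 58.46%. The plan states 58.5%, so this is how the plan itself uses the outcome.

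**2. Apply it at the 65% target.**
- School: 0.03 × 0.95 × 0.40 = 0.0114, or 11.4 wearers per 1,000 screened. Cost per wearer is 1.30/0.0114 = US$114.04.
- Referral: 0.03 × 0.65 × 0.40 = 0.0078, or 7.8 per 1,000. Cost per wearer is 0.80/0.0078 = US$102.56, which is 10.1% lower.
- Shortfall in wearers: 1 − 0.65/0.95 = 31.6%. Per arm this is 14,100 × 0.0036 = 50.8 wearers (161 v 110).
- Incremental cost of School: (1.30 − 0.80)/(0.0114 − 0.0078) = US$138.89 per extra wearer.

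**3. Vary acceptance, with wear at 40% in both arms.**

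| Referral acceptance | Referral cost per wearer (US$; School 114.04) | Fewer wearers per child screened | School's cost per extra wearer (US$) |
|---|---|---|---|
| 58.5% | 113.96 | 38.4% | 114.16 |
| 65% | 102.56 | 31.6% | 138.89 |
| 80% | 83.33 | 15.8% | 277.78 |
| 90% | 74.07 | 5.3% | 833.33 |

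**4. Hold the budget fixed instead.** One School arm costs 14,100 × 1.30 = US$18,330. At 65% acceptance that sum buys 18,330/102.56 = 179 wearers under Referral, against 161 under School. The gain is 114.04/102.56 − 1 = 11%.

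**5. Check the listed wear outcome.** Among recipients it is 40% in both arms by assumption, whatever the acceptance. It cannot show the differences in the table.

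**6. Check whether an interval for the incremental ratio would be stable.** Assume 9 children in need per school (300 × 0.03), 47 schools per arm, and the plan's ICC of 0.20 applied to wear. The design effect is 1 + 8 × 0.20 = 2.6 on 423 children per arm. At 65% acceptance the wearer proportions among those in need are 0.38 and 0.26. The standard error of the difference is √[(0.38 × 0.62 + 0.26 × 0.74) × 2.6/423] = 0.051. By a normal approximation about 1% of resamples would have a difference at or below zero. The same calculation gives about 13% at 80% acceptance and 35% at 90%. A percentile interval for the ratio therefore becomes unreliable as uptake approaches the result that the plan hopes for.

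**The case against.** The strongest reply is that the plan concerns scale-up under constraint. The background stresses scarce refractionists and children not yet reached. If savings can be spent on further schools at the same unit cost, cost per wearer is a sensible criterion, and step 4 shows Referral then reaching more children. This stands. A reader might infer that the ratio is the wrong primary outcome, or that a Referral win means fewer children helped overall. The documents support neither reading: the shortfall is per child screened and reverses per dollar. However, the plan does not state which of the two settings applies.

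The ratio also penalises low uptake. The plan names compliance with referral as its main driver and gives a break-even below which Referral loses. This stands too, but the break-even itself allows a Referral win with about 38% fewer wearers.

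A reader might also infer that half of the trial's aim goes untested. That is too strong. Comparable uptake is background wording. The primary hypothesis in the Data Analytic Plan asks only that uptake improve enough for Referral to be more cost-effective, uptake enters the primary denominator, and attendance and receipt are recorded. What is missing is a listed outcome and a planned between-arm comparison that would support the background wording.

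Finally, the 32% is one scenario. Teacher contact about spectacle compliance could raise wear in the Referral groups. At 65% acceptance the gap would close if wear among Referral recipients reached 0.40 × 0.95/0.65 = 58.5% (that this equals the break-even figure is a coincidence). This is a reason to report the difference in wearers, since it may not match the planning value.

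**Conclusion.** The concern holds as a gap in the planned comparisons; the primary outcome itself can stay. On the scenario that the trial is powered to call a Referral win, Referral has the better ratio (US$103 v US$114) with 32% fewer wearers per child screened. The shortfall is 16% at 80% acceptance and 5% at 90%. No listed outcome would show it.

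The percentages rest on 95% receipt in School and equal wear among recipients, and do not depend on prevalence or unit costs. The dollar figures, including US$139 per extra wearer and the 11% advantage of Referral under a fixed budget, treat US$1.30 and US$0.80 as fixed per child screened. Programme cost in the plan includes spectacles, which vary with uptake, so these figures are illustrative. Which model is preferable depends on the value of an extra wearer and on whether savings can be reused, and the ratio alone answers neither.

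**What to change.** Keep cost per wearer as the primary outcome and add the following to the Data Analytic Plan and Outcome Measures.

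1. For each pair of arms, report the difference in programme cost and the difference in wearers per 1,000 screened, with 95% intervals from resampling whole schools within the randomisation strata.
2. Show the joint result on the cost-effectiveness plane, or as net benefit over a range of values per extra wearer. Give the incremental ratio as a point estimate only, without a percentile interval when the wearer difference may include zero.
3. Add two secondary outcomes among all enrolled children: receipt of spectacles before the 3-month visit, and wear at that visit. Exclude spectacles handed out at closeout. Report the between-arm difference with a cluster-adjusted 95% interval.
4. State that this denominator is children who fail screening, not children who need spectacles, so the rates will not match the planning values of 95% and 65%. It is a fair denominator because entry is assessed in the same way in all arms.
5. Limit any statement on comparable uptake to what that interval supports.

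No new data collection should be needed, since the primary outcome already requires receipt and wear to be known in every arm. The cost is slightly more analysis and a conclusion less simple than one winning ratio.
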